8.1 Monitoring

R-Pharm's designees will perform all monitoring functions within this clinical study. The designee's monitors will work in accordance with established SOPs and have the same rights and responsibilities as monitors from R-Pharm. Monitors will establish and maintain regular

contact between the Investigator and R-Pharm. There will be both blinded and unblinded monitors, as appropriate.

Monitors will evaluate the competence of each study site, informing R-Pharm about any problems relating to facilities, technical equipment or medical staff. During the study, monitors will check that written informed consent has been obtained from all subjects correctly and that data are recorded correctly and completely. Monitors are also entitled to compare entries in eCRFs with corresponding source data and to inform the Investigator of any errors or omissions. Monitors will also control adherence to the protocol at the study site. They will arrange for the supply of investigational product and ensure appropriate storage conditions are maintained.

Monitoring visits will be conducted according to all applicable regulatory requirements and standards. Regular monitoring visits will be made to each study site while subjects are enrolled in the study. The monitor will make written reports to R-Pharm on each occasion contact with the Investigator is made, regardless of whether it is by phone or in person.

During monitoring visits, entries in the eCRFs will be compared with the original source documents (source data verification). Please refer to the Monitoring Plan for further details.

Data Management/Coding

Data generated within this clinical study will be handled according to the relevant SOPs of the Data Management and Biostatistics departments of R-Pharm's designee.

An EDC system will be used for this study, meaning that all eCRF data will be entered in electronic forms at the study site. Data collection will be completed by authorized study site staff designated by the Investigator. Appropriate training and security measures will be completed with the Investigator and all authorized study site staff prior to the study being initiated and any data being entered into the system for any study subjects.

All data must be entered in English. The eCRFs should always reflect the latest observations on the subjects participating in the study. Therefore, the eCRFs are to be completed as soon as possible during or after the subject's visit. To avoid inter-observer variability, every effort should be made to ensure that the same individual who made the initial baseline determinations completes all efficacy and safety evaluations. The Investigator must verify that all data entries in the eCRFs are accurate and correct. If some assessments are not done, or if certain information is not available or not applicable or unknown, the Investigator should indicate this in the eCRF. The Investigator will be required to electronically sign off on the clinical data.

The monitor will review the eCRFs and evaluate them for completeness and consistency. The eCRF will be compared with the source documents to ensure that there are no discrepancies between critical data. All entries, corrections and alterations are to be made by the responsible Investigator or his/her designee. The monitor cannot enter data in the eCRFs. Once clinical data of the eCRF have been submitted to the central server, corrections to the data fields will be audit trailed, meaning that the reason for change, the name of the person who performed the change, together with time and date will be logged. Roles and rights of the study site staff responsible for entering the clinical data into the eCRF will be determined in advance. If additional corrections are needed, the responsible monitor or Data Manager will raise a query in the EDC application. The appropriate study site staff will answer queries sent to the Investigator. This will be audit trailed by the EDC application meaning that the name of investigational staff, time and date stamp are captured.

The eCRF is essentially considered a data entry form and should not constitute the original (or source) medical records unless otherwise specified. Source documents are all documents used by the Investigator or hospital that relate to the subject's medical history, that verify the existence of the subject, the inclusion and exclusion criteria and all records covering the subject's participation in the study. They include laboratory notes, ECG results, memoranda, pharmacy dispensing records, subject files, etc.

The Investigator is responsible for maintaining source documents. These will be made available for inspection by the study monitor at each monitoring visit. The Investigator must submit a completed eCRF for each subject who receives study treatment, regardless of duration. All supportive documentation submitted with the eCRF, such as laboratory or hospital records, should be clearly identified with the study and subject number. Any personal information, including subject name, should be removed or rendered illegible to preserve individual confidentiality.

Electronic case report form records will be automatically appended with the identification of the creator, by means of their unique User ID. Specified records will be electronically signed by the Investigator to document his/her review of the data and acknowledgement that the data are accurate. This will be facilitated by means of the Investigator's unique User ID and password; date and time stamps will be added automatically at time of electronic signature. If an entry on an eCRF requires change, the correction should be made in accordance with the relevant software procedures. All changes will be fully recorded in a protected audit trail, and a reason for the change will be required.

Adverse events and medical history will be coded using the most recent version of the Medical Dictionary for Regulatory Activities (MedDRA). Concomitant medications will be coded using the World Health Organization Drug Dictionary Enhanced (WHO DDE).

8.2 Quality Assurance Audit

Study sites, the study database, and study documentation may be subject to Quality Assurance audit during the course of the study by R-Pharm or R-Pharm's designee on behalf of R-Pharm. In addition, inspections may be conducted by regulatory bodies at their discretion.

9. STATISTICS

9.1 Determination of Sample Size

Given that the study would be considered successful if at least 1 of the 2 OKZ dose regimens is shown to be efficacious and that a priori both OKZ dose regimens are assumed to be efficacious, we are using disjunctive power (i.e., a probability of detecting a significant treatment effect for at least 1 OKZ treatment regimen), as a criterion for the estimation of the sample size. Sample size requirements are calculated to provide sufficient disjunctive power to evaluate the primary endpoint (ACR20 response rate at Week 12) and the first secondary endpoint (DAS28 [CRP] <3.2 at Week 12). Sample size was estimated taking into account a multiplicity control procedure and the resulting α adjustment that will be used in this study to control an overall Type I error rate in the strong sense at a 1-sided $\alpha = 0.025$ across the primary and secondary endpoints. More specifically, the α -control strategy will be based on using the Bonferroni adjustment for the tests related to each of the 2 OKZ dose regimens versus placebo (i.e., using the 1-sided $\alpha = 0.0125$ for each dose). A gate-keeping strategy will be used for tests associated with the primary and secondary endpoints for each OKZ dose regimen independently, with a fixed order of hypothesis tests for the primary and secondary endpoints within each OKZ dose regimen. Sample size was estimated based on simulation that implemented the above α adjustment and gate-keeping procedure including the primary endpoint of ACR20 response rate at Week 12 and the first secondary endpoint. Based on this simulation, an adequate sample size was selected to provide sufficient disjunctive power for the primary endpoint and the first secondary endpoint based on DAS28 (CRP) <3.2 rate at Week 12. For the first secondary endpoint, the disjunctive power represents a probability of establishing a significant treatment effect for 1 or 2 OKZ dose regimens for the primary endpoint and a significant treatment effect for 1 or 2 OKZ dose regimens for the first secondary endpoint, conditional on the fact that each dose regimen tested for the secondary endpoint must have null hypothesis previously rejected for the primary endpoint based on a fixed order of testing as per the gate-keeping procedure.

Treatment effect assumptions used in the simulation-based sample size calculations, involving the primary and the first secondary endpoint are as follows.

The ACR20 response rate at Week 12 for the placebo group is estimated to be 25% in this study population (Genovese et al, 2008; Keystone et al, 2004; Weinblatt et al, 2003). The OKZ ACR20 response rates for 64 mg q4w and q2w treatment groups at Week 12 are expected to be at least 50% and 55% respectively, resulting in an expected difference in ACR20 response rates of 25 and 30 percentage points between respective OKZ treatment groups and placebo.

The DAS28 low disease activity (based on DAS28 [CRP] <3.2) response rate at Week 12 is estimated to be 10% in the placebo group (van der Heijde et al, 2006) and 22% and 30% in 64 mg q4w and q2w OKZ treatment groups respectively, resulting in an expected difference of 12 and 20 percentage points between respective OKZ treatment groups and placebo.

The references cited above for ACR20 and DAS28 response rates are assumed to reflect approximately 10% of subjects discontinuing randomized treatment prior to Week 12. In this study, subjects who discontinue prior to Week 12 will be classified as nonresponders for the primary endpoint of ACR20 at Week 12 as well as for the secondary endpoint of DAS28 (CRP) <3.2 at Week 12.

The primary endpoint as well as the secondary endpoints that are binary in nature will be analyzed using a 2×2 chi-squared test for equality of proportions for each OKZ treatment group compared with placebo.

Based on the treatment effect assumptions and the methodology for estimating sample size via simulation to ensure sufficient disjunctive power as described above, a sample size of 420 subjects randomized in a 1:1:1 ratio (140 subjects per treatment group) will yield 100% disjunctive power for testing the primary hypothesis (ACR20 at Week 12) and 98% disjunctive power for the evaluation of the secondary endpoint of DAS28 (CRP) <3.2 rate at Week 12.

9.2 Data to be Analyzed

Data handling will be the responsibility of R-Pharm's designee. The data will be inspected for inconsistencies by performing validation checks.

9.3 Analysis Populations

- Intent-to-treat (ITT) population: The ITT population will include all randomized subjects. Subjects will be analyzed according to the treatment group to which they were randomized. The ITT population will be the primary analysis population.
- Modified Intent-to-treat (mITT) population: The mITT population will include all randomized subjects who receive at least 1 dose of study treatment. Subjects will be analyzed according to the treatment group to which they were randomized. The mITT population, if sufficiently different from the ITT population (>5% of ITT subjects excluded from the mITT population across all treatment groups), will be used for supportive analyses of the primary and secondary efficacy endpoints.
- Per Protocol (PP) population: The PP population will include all ITT subjects who do not have any major protocol violations. Subjects will be analyzed according to the

treatment group to which they were randomized. Major protocol violations will be defined and the inclusion of subjects in the PP population will be finalized prior to study unblinding. The PP population will be used for supportive analyses of the primary and secondary efficacy endpoints.

- Safety population: The safety population will include all subjects who receive at least 1 dose of study treatment. Subjects in the safety population will be analyzed according to the treatment they actually received. In addition to the primary safety analysis, the incidence of AEs will be analyzed separately for subjects administered an additional DMARD as rescue medication during the Treatment Period and for subjects who did not receive rescue medication.
- Pharmacokinetic population: The PK population will include all subjects who receive at least 1 dose of OKZ and have sufficient plasma samples for PK assessments without important protocol deviations or events affecting the PK results. All subjects in the PK population must have at least 1 evaluable postdose OKZ concentration. To be included in the PK subpopulation, subjects must have received at least 1 dose of OKZ, received OKZ on Week 0, and have sufficient plasma samples to allow calculation of at least 1 PK parameter.

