The CREDO 1 study includes a 4-week Screening Period, a double-blind Treatment Period from Week 0 to Week 24, and a Safety Follow-Up Period from Week 24 to Week 44.

Subjects will be assessed for eligibility to enter the study during a 4-week Screening Period. At randomization, a total of 420 eligible subjects will be randomly assigned to 1 of 3 treatment groups in a 1:1:1 ratio:

1. OKZ 64 mg q4w: SC injection of OKZ 64 mg q4w (alternating with SC injection of placebo OKZ q4w to maintain blinding) + MTX.
2. OKZ 64 mg q2w: SC injection of OKZ 64 mg q2w + MTX.
3. Placebo: SC injection of placebo q2w + MTX.

Throughout the double-blind Treatment Period, all subjects will be required to remain on a stable dose of background MTX at 15 to 25 mg/week (or ≥ 10 mg/week if there is documented intolerance to higher doses) with a stable route of administration, and concomitant treatment with folic acid ≥ 5 mg per week or equivalent is required for all subjects. The last dose of study treatment (OKZ or placebo) will be at Week 22 in all groups. Following Visit 2 (randomization), subjects will return to the study site at least every other week through Week 24 for response and safety assessments as per the study Schedule of Events. Blood samples to assess

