- Safety population: The safety population will include all subjects who receive at least 1 dose of study treatment. Subjects in the safety population will be analyzed according to the treatment they actually received. In addition to the primary safety analysis, the incidence of AEs will be analyzed separately for subjects administered an additional disease-modifying anti-rheumatic drug (DMARD) as rescue medication during the period of treatment without rescue medication and with rescue medication.
- Pharmacokinetics population: The PK population will include all subjects who receive at least 1 dose of OKZ and have sufficient plasma samples for PK assessments without important protocol deviations or events affecting the PK results. All subjects in the PK population must have at least 1 evaluable postdose OKZ concentration. To be included in the sample-rich PK subpopulation, subjects must have received at least 1 dose of OKZ, received OKZ on Week 0, and have sufficient plasma samples to allow calculation of at least 1 PK parameter.

Efficacy Analysis

Efficacy analyses will be conducted using the ITT population. Supportive analyses of the primary and secondary efficacy endpoints will also be conducted using the mITT (if sufficiently different from the ITT population) and PP populations. All comparisons for efficacy assessments will be carried out based on treatment groups to which the subjects were originally randomized.

No adjustment for covariates will be included in the primary analysis of the primary endpoint or the analysis of the secondary and other endpoints that are binary in nature. Analyses of the continuous efficacy endpoints will be adjusted for baseline values of the corresponding parameters.

Endpoints that are binary in nature will be analyzed using a 2×2 chi-squared test for equality of proportions for each OKZ treatment group compared with placebo. Endpoints that are continuous in nature will be analyzed using an analysis of covariance (ANCOVA) model including a fixed effect for treatment and adjusted for the baseline value of the corresponding parameter.

Other statistical methods and models will be used to investigate sensitivity to missing data and adherence to randomized treatment.

Multiplicity Adjustment

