6.13.2 Allowed Medications

The following medications are allowed (non-exhaustive list), including clarifications of the above prohibited medications:

- Inhaled corticosteroids
- Topical corticosteroids
- Oral corticosteroids
 - Doses of ≤ 10 mg/day of prednisone or equivalent are permitted as long as the dose was not changed within the 2 weeks prior to baseline; dose adjustments are not permitted during the study unless the Investigator changes the dose for safety reasons.
- Intra-articular corticosteroids
 - No more than 2 joints may be injected during the study at or after Week 14, after all study assessments for this time point are performed. The cumulative dose for both injections must not exceed 40 mg methylprednisolone or equivalent. Joints treated with IA corticosteroids must be rated with their pre-injection status for the remainder of the study and should be omitted from all subsequent joint assessments (see Sections 7.1.2, 7.1.6, and 7.1.7).
- NSAIDs
 - The subject must have received a stable dose for ≥ 2 weeks prior to baseline, and the dose must be kept constant throughout the entire study unless the Investigator changes the dose for safety reasons.
- Analgesic treatment with paracetamol/acetaminophen is permitted up to a maximum dose of 2000 mg per day (maximum 1000 mg per dose) or up to the maximum dose in the local label, whichever is lower. Paracetamol/acetaminophen are not to be taken within 24 hours prior to joint assessment, including baseline assessment.

6.13.3 Rescue Medication Starting at Week 14

Subjects will be classified in terms of their response to study treatment at Week 14, with nonresponders defined as all subjects who do not improve by at least 20% in both SJC and TJC (66-68 joint assessment). Nonresponders in all groups will be prescribed sulfasalazine and/or hydroxychloroquine according to the local label of the prescribed drug(s) as rescue medication starting at or as close as possible to Week 14, in addition to the assigned study treatment.

The maximum allowed doses of sulfasalazine and hydroxychloroquine are:

- Sulfasalazine: 3 g per day
- Hydroxychloroquine: 400 mg per day

Nonresponders at Week 14 will remain blinded to their assigned treatment. Rescue medication will be administered as open-label treatment. The choice of rescue medication (sulfasalazine, hydroxychloroquine, or both) should be made according to local practice, and the assigned rescue medication regimen should be maintained throughout the study.

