7.6.1 Adverse Events

For the purposes of this study, an AE will be defined as any untoward medical occurrence in a subject or clinical investigation subject administered a pharmaceutical product and which does not necessarily have a causal relationship with this treatment. An AE can therefore be any of the following:

- Any unfavorable and unintended sign, symptom, or disease temporally associated with the use of a medicinal product, whether or not considered related to the medicinal product.
 - If the Investigator determines a laboratory abnormality to be clinically significant, it is considered a laboratory AE; however, if the abnormal laboratory value is consistent with a current diagnosis (or signs or symptoms if a diagnosis is not possible) and is not a clinically significant worsening from the baseline laboratory parameter, it should be documented accordingly without being reported as a separate laboratory AE.
- Any new disease or exacerbation of an existing disease (a worsening in the character, frequency, or severity of a known condition).

The Investigator is responsible for recording all AEs observed during the study from the time the subject signs the ICF. All AEs are recorded throughout the study until the last visit of the subject. The Investigator is responsible for the appropriate medical care of the subjects during the entire study.

Each AE is to be evaluated for duration, severity, seriousness, and causal relationship to the investigational drug. For all AEs, the Investigator must pursue and obtain information adequate both to determine the outcome of the AE and to assess whether it meets the criteria for classification as an SAE. The Investigator is required to assess causality as described below. For AEs with a causal relationship to the study treatment, follow-up by the Investigator is required until the event has resolved, it has a stable sequelae, the Investigator determines that it is no longer clinically significant, or the subject is lost to follow-up.

Severity

The severity of AEs will be characterized according to the CTCAE grades and definitions summarized in Table 6.

Table 6 CTCAE Grades and Corresponding AE Severity

CTCAE Grade	Corresponding AE Severity
Grade 1	Mild; asymptomatic or mild symptoms; clinical or diagnostic observations only; intervention not indicated
Grade 2	Moderate; minimal, local, or noninvasive intervention indicated; limiting age-appropriate instrumental ADL

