9.4.15 Safety Analyses

Analysis of safety endpoints (see Section 4.7) will be done based on the safety population. Subjects in the safety population will be analyzed according to the treatment they actually received. Additionally to the primary safety analysis, the incidence of AEs will be analyzed separately for subjects administered additional DMARDs as rescue medication during the period of treatment without rescue medication and with rescue medication.

Major components for the safety analysis will include:

- AEs will be solicited at every study visit, recorded, and coded according to the most recent version of the MedDRA.
- SAEs.
- Vital signs and physical examination findings.
- Laboratory parameters.
- ECG and other specialized tests findings.

All safety assessments will be summarized in a descriptive manner. Further details will be provided in the SAP.

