9.4.15.1 Adverse Events

All AEs will be analyzed in terms of descriptive statistics and qualitative analysis. Adverse events will be listed for each subject and summarized by SOC and PT according to the most recent version of the MedDRA. In addition, summaries of AEs by severity (evaluated using the CTCAE version 4.0) and relationship to study treatment will be presented. All safety and tolerability data recorded during the study will be listed and summarized by treatment group, and over time, as appropriate. Additionally to primary safety analysis, the incidence of AEs

will be analyzed separately for subjects administered additional DMARD as rescue medication during the period of treatment without rescue medication and with rescue medication.

Treatment-emergent AEs are defined as AEs that first occurred or worsened in severity after the first administration of the study treatment. Adverse event summaries will include incidence of TEAEs, SAEs including deaths, AEs that led to study treatment discontinuation, and AEs by maximum severity and relationship to study treatment. All summaries will be presented by MedDRA SOC and PT for each treatment group.

Safety/tolerability and AE data will be presented in individual listings.

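### Section 9.3 and the safety sections define the rescue-medication AE analysis differently, and the by-period version sets about 14 weeks against about 10 with no exposure adjustment named

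*Combined protocol and SAP*

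**What the plan says.** Four places in the current text describe a supplementary AE analysis related to rescue medication.

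- Section 9.3, Safety population: AE incidence is analysed separately for subjects "administered an additional DMARD as rescue medication during the Treatment Period and for subjects who did not receive rescue medication". This divides subjects into two groups.
- Synopsis, Safety population: AE incidence is analysed for subjects given a DMARD "as rescue medication during the period of treatment without rescue medication and with rescue medication". This divides the time of rescued subjects.
- Section 9.4.15: AE incidence is analysed "separately for subjects administered additional DMARDs as rescue medication during the period of treatment without rescue medication and with rescue medication".
- Section 9.4.15.1 repeats the by-period split.

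On timing, Section 6.13.3 has nonresponders prescribed sulfasalazine and/or hydroxychloroquine "as rescue medication starting at or as close as possible to Week 14, in addition to the assigned study treatment". The synopsis describes "a double-blind Treatment Period from Week 0 to Week 24, and a Safety Follow-Up Period from Week 24 to Week 44". Section 7.6.1 adds: "All AEs are recorded throughout the study until the last visit of the subject". The TEAE definition in Section 9.4.15.1 has a start but no end: "Treatment-emergent AEs are defined as AEs that first occurred or worsened in severity after the first administration of the study treatment".

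Safety summaries are descriptive, and Section 9.4.15 leaves further detail to the SAP. The text available has no person-time denominator for this analysis, no rule assigning an AE to one period or the other, and no stated end of the with-rescue period. Section 9.4.5 defines duration of exposure from first to last dose. It does not split that duration at rescue or use it as an AE denominator.

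**The concern.** A programmer who follows Section 9.3 and one who follows Section 9.4.15 will produce tables with different subjects, time windows and meaning. The synopsis and Section 9.3 disagree on the definition of the same population, so this is more than a variation in wording.

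Each version also has its own reading problem. Under Section 9.3, everything a rescued subject reports from Week 0 counts under rescue, although rescue cannot start until about Week 14. Under the by-period version, the two periods have different lengths. If incidence is reported as the share of subjects with at least one AE, the shorter period gives the lower figure whether or not rescue affects safety. A reader could then conclude that adding a DMARD left AE frequency unchanged or lowered it, when the difference comes only from the calendar.

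**Working it through.** The plan states no figure for this analysis, so there is none to reproduce. The check sets the texts side by side and then works out what unequal periods do to a simple percentage.

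**1. The two definitions**

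| | Section 9.3 | Synopsis, 9.4.15, 9.4.15.1 |
|---|---|---|
| Subjects | Rescued and not rescued | Rescued only |
| Split | Between subjects | By period within subject |
| AEs before rescue in rescued subjects | Counted under rescued | Counted under the period without rescue |

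**2. Period lengths from the plan**

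- Without rescue: Week 0 to about Week 14, so about 14 weeks.
- With rescue, to the end of treatment: 24 − 14 = about 10 weeks.
- Ratio of with to without: 10/14 = 0.71.
- Under Section 9.3, a rescued subject followed to Week 24 has 14/24 = 58% of that time before rescue, all of it labelled rescued.

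**3. Simple percentages with no rescue effect**

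Assumptions, none of them from the plan: AEs occur at a constant rate λ per week, the same before and after rescue; each rescued subject contributes the full 14 and 10 weeks; a subject counts in a period if at least one AE starts in it. With an assumed 24-week incidence p:

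- λ = −ln(1 − p)/24
- incidence over t weeks = 1 − exp(−λt)

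For p = 50%: λ = 0.6931/24 = 0.0289 per week.

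- Without rescue: 1 − exp(−0.0289 × 14) = 33.3%
- With rescue: 1 − exp(−0.0289 × 10) = 25.1%

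| Assumed 24-week incidence | Without rescue, 14 weeks | With rescue, 10 weeks |
|---|---|---|
| 10% | 6.0% | 4.3% |
| 30% | 18.8% | 13.8% |
| 50% | 33.3% | 25.1% |
| 70% | 50.5% | 39.4% |

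**4. The same data per unit of time**

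At p = 50% the rate in both periods is 0.0289 × 52 × 100, or about 150 events per 100 patient-years. The difference in step 3 disappears because it came only from period length.

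**The case against.** The strongest reply is that this is a supplementary, descriptive table whose details are left to a SAP finalised before unblinding. The protocol never says the percentage will be unadjusted, and Section 9.4.15.1 allows summaries over time as appropriate. That stands as far as it goes: the plan leaves the measure unspecified; it does not choose a wrong one. Nor does it say the analysis is meant to show whether adding a DMARD changes the safety of OKZ. That purpose is an inference, and rescue is given in all arms, including placebo. But leaving detail to a SAP does not reconcile two conflicting definitions within the protocol.

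Three stronger readings are tempting and are not supported.

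- *The with-rescue period runs to Week 44.* That would be 30 weeks and, at p = 50%, 1 − exp(−0.0289 × 30) = 58.0%, which reverses the direction. Sections 9.4.15 and 9.4.15.1 refer to a period of treatment, and treatment ends at Week 24, so Week 24 is the natural end. The end should still be written down, because AEs are recorded to the last visit.
- *Section 9.3 suffers equally from unequal time at risk.* Subjects followed to Week 24 have the same time at risk whether rescued or not. A gap (50% versus 41.6% to 48.1%) appears only if 5% to 15% are assumed to leave the study before Week 14. The 10% in Section 9.1 is discontinuation of randomized treatment, and those subjects are to stay on study.
- *Section 9.3 compares Week 14 nonresponders with responders.* Its unrescued group also includes anyone who left before Week 14 or was not prescribed rescue.

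The assumed incidences are illustrations. In RA0056 (Section 2.2.3.2), 63.6% to 87.0% of subjects per OKZ or placebo group had TEAEs, follow-up included, so the figure for any AE may lie near or above the top of the range. A constant rate is also a simplification: person-time removes the effect of period length but not a genuine change in AE frequency between early and late treatment.

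**Conclusion.** The inconsistency is established by the text: Section 9.3 stands alone against the synopsis, 9.4.15 and 9.4.15.1. Under Section 9.3, about 14 weeks of pre-rescue AEs are counted under rescue. Under the by-period version, the imbalance of about 14 weeks against about 10 is built into the design. If a simple percentage is used, it creates an apparent difference of about 8 percentage points at an assumed 24-week incidence of 50%, and from about 2 to 11 points across 10% to 70%, with no rescue effect. These sizes depend on the constant-rate assumption and a Week 24 cut-off.

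This is a minor point. It affects one additional descriptive safety table and leaves the primary safety analysis, efficacy conclusions, alpha and sample size as they are.

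**What to change.** Before unblinding:

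1. Reconcile Section 9.3 with the synopsis, 9.4.15 and 9.4.15.1, either by a minor protocol correction or by a SAP statement of which definition governs.
2. Assign each AE to a period by its onset date relative to the first rescue dose.
3. State where the with-rescue period ends.
4. Split person-time at the first rescue dose and report events per 100 patient-years by period and treatment arm.
5. If never-rescued subjects from Week 14 onward are shown, label them as descriptive context only. Rescue is determined by nonresponse, so they are not a fair comparison group.

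No new data are needed. The cost is the wording change and slight extra programming.
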